13.2.3 Comparison of Validation Set to Ground Truth Histology

First, an expert reviewer and 2 comparative reviewers will assess each of the VIO images, blinded to the histopathology results. For each area, the reviewer will classify the predicted primary histopathology characteristics according to the categories described in section 11.4. Second, the expert reviewer will determine the actual primary histopathology characteristics based on the histopathology results. Third, the predicted characteristics will be compared to the expert reviewer classification.

An iterative review process will be performed until there is complete consensus across all reviewers. The output of this iterative review process will be an “answer key” that reflects 100% consensus of the comparative results from the VIO image and pathology across all 3 comparative readers. Achieving 100% agreement/concensus through this process satisfies the first Primary Endpoint.

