11.3 Image Analysis Stage

The Image Analysis stage includes the following three phases:

1. Development of consensus training materials by three (3) Comparative Readers
2. Validation of Enspectra Health Images with Ground Truth Pathology by three (3) Comparative Readers
3. Performance testing (Blinded Reader assessment of Enspectra Health images)

11.3.1 *Phase 1: Training/Consensus*

1. Three Comparative Readers (CRs) will train as a group using the [REDACTED] VIO images and all available pathology slides. Comparative readers will assess a minimum of [REDACTED] [REDACTED]. VIO images from 20 lesions on 20 subjects meeting the requirements described above in Tables 1-5 will be evaluated for this training assessment.
2. CRs will label the images [REDACTED]
[REDACTED]
[REDACTED]
[REDACTED]
[REDACTED]
3. Images will be marked as elements are identified but exhaustive annotation is not required. Samples will be reviewed until complete consensus achieved. Secondary histopathology characteristics will also be evaluated and recorded.
4. The output of this phase of the study will be a set of 20 training samples consisting of matched VIO images and ground truth pathology slides.

11.3.2 *Phase 2: Validation* (VIO Image Assessment in Comparison with Ground Truth Pathology) and Establishment of an “Answer Key”

1. A total of 30 VIO images from 30 subjects meeting the requirements described above in Tables 1-5 will be evaluated in this validation assessment.
2. Two experienced physicians with dermatopathology expertise will serve as the primary CRs. A third expert CR, with RCM experience, will adjudicate discrepancies between the two primary CRs.
3. Two primary CRs will assess the [REDACTED] VIO images and predict histology.
[REDACTED]
[REDACTED]
4. The expert CR will review all pairs and will work with the two primary CRs until complete consensus achieved (i.e., until 100% VIO image v. ground truth pathology achieved across all 3 CRs). Achieving 100% agreement/consensus at the completion of this process represents success for Primary Endpoint 1: 100% agreement and validation of specific tissue features on VIO images (epidermis, dermis, collagen, blood vessels and pigment) in comparison to gold standard pathology images in Comparative Reader assessment.

5. The output of this validation process will establish the answer key for the performance testing assessment.

11.3.3 *Phase 3: Performance Testing* (VIO Image Assessment by Readers Blinded to Pathology Results)

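### The Endpoint 2 answer key is a joint VIO-and-pathology consensus with no visible lock on the pathology read, so blinded-reader accuracy is not shown against an independent, fixed pathology reference

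*Combined protocol and SAP*

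**What the plan says.** Sections 8.2 and 11.3.3 define Primary Endpoint 2 as more than 90% agreement between the blinded readers and the answer key. Section 13.2.4 scores accuracy against that key, for primary characteristics only, with a 90% target for the point estimate.

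Section 13.2.3 builds the key in four steps:

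1. "First, an expert reviewer and 2 comparative reviewers will assess each of the VIO images, blinded to the histopathology results".
2. "Second, the expert reviewer will determine the actual primary histopathology characteristics based on the histopathology results".
3. "Third, the predicted characteristics will be compared to the expert reviewer classification".
4. "An iterative review process will be performed until there is complete consensus across all reviewers".

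The resulting key is one that "reflects 100% consensus of the comparative results from the VIO image and pathology across all 3 comparative readers".

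Section 11.3.2 describes the same phase differently. It says "Two primary CRs will assess the [REDACTED] VIO images and predict histology", and redacted lines follow. It then says "A third expert CR, with RCM experience, will adjudicate discrepancies between the two primary CRs". The expert also goes through every image-slide pair with the two primary readers until VIO image and pathology agree completely for all three. Finally, "The output of this validation process will establish the answer key for the performance testing assessment".

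**The concern.** A reference standard should not depend on the test it is used to judge. Here the reference for a primary endpoint comes out of a discussion in which the VIO images are one of the two inputs, and that discussion ends only when image reading and pathology coincide. If a pathology label can be changed to reach agreement, the index images help to form their own reference (incorporation bias).

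The expert's role adds to this. Under 13.2.3 the person who sets the pathology truth has already committed to a VIO reading of the same lesion, and one of the three predictions is then compared with a classification by the same person. Under 11.3.2 the expert is not named as a predictor. A site or reader charter could follow either section and produce a different key.

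What is at stake is how an Endpoint 2 result can be read. A figure just above 90% could reflect agreement with pathology, or agreement with a key that had shifted toward the images. The visible plan keeps no record that would tell the two apart.

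**Working it through.** **Roles, side by side**

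| Question | 11.3.2 | 13.2.3 |
|---|---|---|
| Who predicts from VIO images | Two primary readers named (redacted text follows) | Expert and two comparative readers |
| Who sets the pathology truth | Not stated in visible text | Expert, after predicting |
| Expert's part in consensus | Adjudicates, goes through all pairs, works with the others to full agreement | One of the readers who must agree |
| Pathology read fixed before comparison | Not stated in visible text | Not stated |
| Which read may change | Not stated in visible text | Not stated |
| Pre-consensus reads reported | Not stated in visible text | Not stated |

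**What the iteration allows.** A disagreement between a prediction and the step-2 pathology classification can be settled in two ways.

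- The prediction is changed. The key then equals the expert's pathology read and there is no inflation.
- The pathology label is changed. The key then moves toward the comparative readers' VIO reading.

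The visible text excludes neither.

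**Plan figures.** The documents give no expected agreement with pathology and no relabelling rate, so there is no plan figure for the bias to reproduce. The only precision figure is ±6.2% for 360 independent areas (13.1). At 90% the half-width is 1.96 × √(0.9 × 0.1 / 360) = 3.1%, so 6.2% matches the full width. That is a separate matter and does not bear on this point.

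**Upper-bound illustration**

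Inputs from the documents: 360 areas (13.1, 13.2.4) and a 90% target (13.2.4). Assumed inputs:

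- a = a blinded reader's true agreement with the pathology read;
- f = the share of that reader's discordant areas whose key label is moved to the reader's answer.

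Agreement with the key = a + (1 − a) × f.

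The f needed for 90% = (0.90 − a) / (1 − a). Areas needed = (0.90 − a) × 360.

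| Assumed a | Discordant areas of 360 | f needed | Areas relabelled in the reader's favour |
|---|---|---|---|
| 88% | 43.2 | 0.167 | 7.2 |
| 85% | 54 | 0.333 | 18 |
| 80% | 72 | 0.50 | 36 |

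At a = 85%, f = 0 gives 85.0%, f = 0.25 gives 88.75% and f = 0.50 gives 92.5%.

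This is an upper bound because every change is assumed to help. If a share g of the reader's concordant areas is relabelled away from the reader's answer, the expression becomes a + (1 − a) × f − a × g. For example, at a = 85% (306 of 360 areas), 18 changes in favour and 18 against give (306 + 18 − 18) / 360 = 85%, so nothing is gained.

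**The case against.** The strongest reply is that pathology plainly governs. Section 13.2.3 treats the expert's slide reading as the actual state and the VIO readings as predictions, compares the second with the first, and nowhere says that a pathology label is altered to fit an image. This stands in part. A reader might infer that Endpoint 2 is not measured against pathology at all, or that the key is in fact revised toward the images. The documents support neither: the key starts from and includes pathology, and revision of the pathology label is left open, not prescribed.

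A reader might also infer that any such revision must raise blinded-reader agreement. It need not. Labels would move toward the comparative readers' VIO reading, and the blinded readers are a different group. Where a blinded reader had matched pathology, the change counts against that reader.

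The illustration has limits too. Moving 85% to 90% means relabelling a third of all discordant areas, each in the reader's favour. Scoring is in points under section 11.5, which is not in the public text, and a mixed model is fitted to one record per patient per reader. One area therefore need not carry 1/360 of the estimate.

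The text is also incomplete. Lines are redacted in 11.3.2 just where an order of unblinding could sit, and 11.4 and 11.5 are cited but absent. A locking rule may exist there. The redaction also narrows the contradiction: 11.3.2 names two predictors but does not say in visible words that the expert makes no prediction.

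Finally, if areas are defined on the VIO image, the expert may be unable to label them from slides without seeing that image at all. This is a fair limit on the remedy, and the fix allows for it.

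**Conclusion.** The point holds in this form. The Endpoint 2 reference is a joint VIO-and-pathology consensus driven to 100% agreement, and the visible text does not fix the pathology classification beforehand. Blinded-reader accuracy is therefore not shown against an independent, fixed pathology reference. The two accounts of the expert's part differ and must be reconciled; that the expert predicts before setting the truth rests on 13.2.3 alone.

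The size and direction of any bias cannot be determined from the documents. The 7, 18 and 36 areas are upper-bound figures on assumed starting values of 88%, 85% and 80%, with equal weight per area and every change favourable. They show only that a modest number of changes could decide a 90% point-estimate target. The conclusion is conditional on no lock being present in the redacted or unpublished sections.

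**What to change.** Reconcile 11.3.2 and 13.2.3 as follows.

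- The two primary comparative readers make the blinded VIO predictions.
- The expert sets the pathology classification without first predicting from that lesion's VIO images, using them only as far as needed to locate the areas on the slide.
- The step-2 pathology classification is frozen before the comparison.
- Each later change to the key is logged with its reason and its direction (toward the VIO reading or not).
- Agreement before consensus is reported.
- Endpoint 2 is reported against the frozen classification as well as against the final key.

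Keeping the final key preserves legitimate corrections, such as a wrongly matched area, and makes them visible. If a locking rule already exists in text that is not public, a citation to it in 13.2.3 answers the locking question; the expert's role still needs to read the same in both sections.

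The cost is wording in the SAP and reader instructions, a change log and one extra scoring run, with no additional reader. The downside for the sponsor is a possibly less favourable second figure.

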1. Three Blinded Readers (BR) will be trained using the training set developed in Phase 1. Training materials may also be supplemented with other data sets [REDACTED]
[REDACTED]
2. The Phase 2 Validation Set and the answer key derived from such will be used for the BR assessment. BRs will assess [REDACTED]
Assessment of performance of the BRs defines the success of Primary Endpoint 2: >90% agreement between Blinded Reader VIO image assessment and answer key developed from validation assessment.

12 Study Procedures

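### Primary Endpoint 1 is met by construction: the readers iterate until VIO and pathology agree 100%, and reaching that point is counted as success

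*Combined protocol and SAP*

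**What the plan says.** Sections 3 and 8.2 make 100% agreement of tissue features between VIO images and pathology, in the Comparative Reader assessment, the first primary endpoint.

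Section 11.3.2 (Phase 2) has two primary CRs predict histology from the VIO images. The expert CR then works with them "until 100% VIO image v. ground truth pathology achieved across all 3 CRs". The success rule follows at once: "Achieving 100% agreement/consensus at the completion of this process represents success for Primary Endpoint 1".

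Section 13.2.3 gives three steps before any iteration: blinded VIO readings, a pathology-based classification by the expert, and a comparison ("Third, the predicted characteristics will be compared to the expert reviewer classification"). It continues: "An iterative review process will be performed until there is complete consensus across all reviewers". It then states: "Achieving 100% agreement/concensus through this process satisfies the first Primary Endpoint".

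The consensus result is carried forward. Section 11.3.2 says: "The output of this validation process will establish the answer key for the performance testing assessment". Section 11.3.3 defines Endpoint 2 as ">90% agreement between Blinded Reader VIO image assessment and answer key developed from validation assessment".

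**The concern.** A primary effectiveness endpoint has to be able to come out differently depending on how well the device performs. Here the readers continue until the target value is reached, and reaching it is the result. The visible text gives no limit on rounds, no category for areas that stay unresolved and no outcome that counts as failure.

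Objective 2 (section 8.1) is that VIO features align with the biopsy pathology. A figure that reads the same after few or many initial disagreements cannot show this.

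The weakness also reaches Endpoint 2. Section 13.2.3 describes the key as one that "reflects 100% consensus of the comparative results from the VIO image and pathology across all 3 comparative readers". Blinded readers are therefore scored against a joint VIO-pathology consensus, and the Endpoint 1 result does not show how closely that key follows pathology alone.

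**Working it through.** **The plan's own figure.** The documents give no hypothesis, threshold below 100%, power or precision for Endpoint 1. The only precision figure for the validation set is the ±6.2% in 13.1, for 360 areas taken as independent. At 90% agreement, 1.96 × √(0.90 × 0.10 / 360) = 3.1 points, so 6.2 points is the full width. It cannot be a half-width under independence: the largest possible half-width, at 50%, is 5.2 points. This does not affect the present point, but the half-widths below should be compared with 3.1.

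**Step 1: stopping rule against success rule.** In 11.3.2 the review stops at 100% VIO-versus-pathology agreement across all three CRs, and success is that same state. In 13.2.3 the review stops at complete consensus, and success is again that state. Given that the review ends as written, the probability of reporting 100% is 1 for any first-pass agreement.

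**Step 2: what the 100% can conceal.** Inputs are 360 areas (at least 360 in 13.1, approximately 360 in 13.2.4) and an assumed first-pass agreement p, for which the documents give no value. One reader's initial disagreements are 360(1−p). If both primary CRs have rate p, the areas where at least one disagreed number 360(1−p) if their errors overlap fully, 360(1−p²) if errors are independent, and 720(1−p) if errors never overlap.

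| p | One CR, or two with full overlap | Two CRs, independent errors | Two CRs, no overlap | Reported |
|---|---|---|---|---|
| 70% | 108 | 183.6 | 216 | 100% |
| 80% | 72 | 129.6 | 144 | 100% |
| 90% | 36 | 68.4 | 72 | 100% |
| 95% | 18 | 35.1 | 36 | 100% |

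The counts scale with the number of areas. Under 13.2.3, where the expert also reads the VIO images, a third reader could only leave them unchanged or raise them.

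**Step 3: would 100% arise without the iteration?** Under a single-pass 100% rule on 360 independent areas, the chance of success is p^360: about 1 × 10⁻⁸ at 95%, 0.027 at 99% and 0.70 at 99.9%. On 30 subject-level calls it is p^30: 0.215 at 95% and 0.740 at 99%. Unless first-pass agreement were almost perfect, it is the iteration that supplies the 100%.

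**Step 4: precision if first-pass agreement is reported instead.** For one reader at 90% observed, with 30 subjects and m areas each, the 95% half-width is 1.96 × √(0.09 × (1 + (m−1) × ICC) / (30m)). Here m = 12 gives 360 areas and m = 20 gives 600. The ICC values, equal areas per subject and m = 20 are assumptions.

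| ICC | 0 | 0.1 | 0.3 | 0.5 | 1 |
|---|---|---|---|---|---|
| m = 12, points | 3.1 | 4.5 | 6.4 | 7.9 | 10.7 |
| m = 20, points | 2.4 | 4.1 | 6.2 | 7.8 | 10.7 |

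Extra areas help little once areas within a subject are correlated. These are overall figures; a feature assessed in fewer areas would have a wider interval.

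**Step 5: an illustrative 90% bar on the lower bound.** A two-sided 95% Wilson lower bound exceeds 0.90 when the observed value exceeds 0.90 + 1.96 × √(0.09/n), with n the effective number of areas. For m = 12:
- ICC 0, n = 360: 93.1%.
- ICC 0.3, n = 360/4.3 = 83.7: 96.4%.
- Complete correlation, n = 30: not attainable, since 30/30 gives a lower bound of 0.886.

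**Step 6: reader roles.** In 11.3.2 two primary CRs predict and the expert adjudicates. In 13.2.3 the expert also reads the VIO images first and then sets the pathology classification. The two accounts differ, and under the second the reference is set by someone who has already read the VIO images.

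**The case against.** Several points on the other side are fair.

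- **The readers might not agree.** If a VIO feature could not be reconciled with pathology, 100% would not be reached. This stands as a condition: the endpoint is met by construction provided disagreements can be resolved. The visible text does not say what happens otherwise.
- **Some text is unseen.** Part of step 3 in 11.3.2 is redacted, and sections 11.4 and 11.5, cited for categories and scoring, are not in the public text. First readings may be recorded or reported there, so the plan cannot be said to lack this. The success rule itself is unredacted in both places.
- **Consensus is a legitimate way to build a reference, and Phase 2 is not empty.** Both are true. Section 13.2.3 already includes a blinded reading and a comparison with pathology. But the success statements point to the end of the iteration, not to that comparison.
- **Endpoint 2 is a real test.** It uses blinded readers and can fail. It still does not measure agreement with pathology alone.
- **The rates are invented, and the interval type matters.** The agreement rates show what 100% could conceal; they are not forecasts. The unattainable bar at complete correlation is for a two-sided 95% bound; a one-sided 95% Wilson bound at 30/30 is 30/(30 + 2.706) = 0.917, which clears 0.90.
- **Prior VIO reading does not prove bias.** The expert's classification is to rest on histopathology. Influence from the earlier reading is a risk, not something shown.

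**Conclusion.** The concern holds, and it must be fixed. Two unredacted passages make the stopping condition the success condition, so a completed Phase 2 reports 100% whether one reader initially disagreed with pathology on 18 or on 108 of 360 areas. The Endpoint 1 figure is not confirmatory evidence for Objective 2. The conclusion rests on the visible text and on disagreements being resolvable. The counts also rest on assumed agreement rates, but the conclusion does not depend on any particular rate. Confidence in the reading of the success rule is high; how first readings are recorded is less certain because of the redactions.

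**What to change.** Amend sections 3, 8.2, 11.3.2 and 13.2.3 as follows.

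1. Keep consensus only as the procedure that builds the answer key, and delete the statements that reaching it is success for Endpoint 1.
2. Define Endpoint 1 as first-pass agreement of each primary CR's blinded VIO classification with the pathology classification, both locked before discussion. Report it by feature and overall with a subject-clustered 95% confidence interval, either as estimation only or against a threshold that the sponsor pre-specifies and justifies. If a threshold is used, state the interval type.
3. Report the number of areas where any reader initially disagreed with pathology, and the number of answer-key entries that differ from the locked pathology classification. Count unresolved areas as disagreements.
4. Reconcile the reader roles in 11.3.2 and 13.2.3 so that whoever sets the pathology reference is not scored and records it without using the VIO readings. If the expert has already read the VIO images, state this as a limitation.

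**Cost.** This redefines a primary effectiveness endpoint, so the protocol and SAP must be amended before Phase 2 reading starts; first readings that were not locked cannot be recovered later. The practical work is to lock, time-stamp and retain the first readings and the pathology classification. No new subjects, images or readers are needed. The reported figure may fall below 100%, and with 30 subjects a threshold on the lower confidence bound could be demanding. Estimation only avoids that second difficulty.

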13.2.4 Performance Testing of Blinded Readers

Once the answer key is finalized for the validation set, 3 blinded readers will be used for performance testing. The blinded readers will be trained using the training set, and will then be provided with the VIO images only from the validation set. Each blinded reader will classify the primary histopathology features and regions for each of the approximately 360 areas in the validation set and identify secondary histopathology characteristics in each VIO image.

Accuracy will be assessed for primary histopathology characteristics only, compared to the answer key, as the proportion of total points for each of the blinded reviewers as described in section 11.5.

The accuracy assessment will be performed using a conditional, generalized linear mixed model (GLMM) to account for correlation among multiple images obtained for the same subject, and for correlation of responses within each reviewer. Once each response has been scored, the data will be condensed to 1 record per patient per reviewer. The dependent variable will be the number of points obtained divided by the maximum number of points possible. The GLMM will use a binomial response distribution and a logit link function. A compound symmetry variance-covariance matrix will be used to account for correlation. Random effects will be included for each subject-reviewer cluster. Reviewer will be included as a model covariate, and the correlation-adjusted proportion correct will be calculated separately for each reviewer by applying the standard logistic function to the least-square means by reviewer. This GLMM framework (with an intercept term) will be used to produce overall and reviewer-specific point estimates and 95% confidence intervals. The point-estimate target for overall accuracy is 90%.

Inter-rater agreement among the BRs will be assessed using Kappa statistics, and the target for agreement is 90%. Overall accuracy compared to the answer key across the subgroups will be assessed by adding each subgroup to the GLMM as a categorical variable. Accuracy for secondary histopathology characteristics may also be reported, but there are no *a priori* targets.

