8.2 Primary Endpoints (Safety and Effectiveness)

- 100% agreement and validation of specific tissue features on VIO images (epidermis, dermis, collagen, blood vessels and pigment) in comparison to gold standard pathology images in Comparative Reader assessment.
- >90% agreement between Blinded Reader VIO image assessment and answer key developed from validation assessment.
- Safety will be assessed as the incidence of all adverse events (analyzed by severity, seriousness, and relationship to the device and procedure) that occur through the 7-day follow-up period.

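### Section 13.2.4 defines blinded-reader accuracy as a proportion of points but estimates it by a conditional GLMM back-transform that runs higher; if the overall figure is built the same way, the 90% target is easier to meet

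*Combined protocol and SAP*

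**What the plan says.** Section 13.2.4 measures accuracy against the answer key "as the proportion of total points for each of the blinded reviewers". Section 8.2 words Primary Endpoint 2 as more than 90% "agreement between Blinded Reader VIO image assessment and answer key developed from validation assessment". Both describe a plain proportion.

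The estimator in 13.2.4 is a different object. Data are reduced to one record per patient per reader (points earned over points possible) and fitted with a binomial, logit-link GLMM that the section calls conditional. "Random effects will be included for each subject-reviewer cluster", and "A compound symmetry variance-covariance matrix will be used to account for correlation". Reader is a covariate, and each reader's proportion correct "will be calculated separately for each reviewer by applying the standard logistic function to the least-square means by reviewer".

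For the overall figure the section says only: "This GLMM framework (with an intercept term) will be used to produce overall and reviewer-specific point estimates and 95% confidence intervals". The success rule is "The point-estimate target for overall accuracy is 90" per cent, with no requirement on a confidence bound.

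The text does not give the overall back-transform, any averaging over the random effects, the fitting method or an expected variance. Scoring is referred to a section 11.5 that is not in the public text.

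**The concern.** The definition and the estimator target different quantities. The proportion of points averages over easy and hard subject-reader combinations. The logistic function of a conditional least-squares mean gives the accuracy for one combination, whose random effect is zero. On the logit scale, at accuracies above 50%, the second is higher.

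Because Primary Endpoint 2 is decided on the point estimate alone, a shift in that estimate acts directly on success. Readers whose share of points is below 90% could be reported as having met the target.

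**Working it through.** **The plan's own figure.** Section 13.1 gives ±6.2% for 360 independent areas. At 90% accuracy, 1.96 × √(0.9 × 0.1 / 360) = 0.031, so 6.2% is the full width. As a half-width it would need p(1 − p) = (0.062/1.96)² × 360 = 0.36, above the maximum of 0.25. The present point does not depend on this; 3.1 points serves only as a yardstick.

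**Direction.** Let the logit for a subject-reader record be μ + b, with b symmetric about zero and SD σ.

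- Planned back-transform: expit(μ).
- Expected proportion of points: E[expit(μ + b)].

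For μ > 0, expit(μ + b) + expit(μ − b) is less than 2·expit(μ) for every b ≠ 0, because the logistic curve is flatter at μ + b than at μ − b. So the proportion of points is below expit(μ) unless σ = 0. With normal b, by 60-point Gauss–Hermite quadrature:

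| σ (logits) | Proportion of points when the back-transform reads 90% | Back-transform when the proportion is 90% | Back-transform when the proportion is 88% |
|---|---|---|---|
| 0.25 | 89.78% | 90.22% | 88.25% |
| 0.5 | 89.11% | 90.85% | 88.94% |
| 0.75 | 88.03% | 91.77% | 89.97% |
| 1.0 | 86.61% | 92.85% | 91.19% |

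**Size in this design.** Inputs from the documents: 30 validation subjects (11.3.2), 3 readers and about 360 areas (13.2.4), hence 360/30 = 12 per subject. Assumptions: one equal-weight point per area, the values of σ, and variance split equally between subject and subject-reader. The fitted model has a reader fixed effect and a random intercept per subject-reader record. The overall estimate is the logistic of the mean of the three reader least-squares means. It was fitted by linearised pseudo-likelihood with REML (PL) and by maximum likelihood with 25-point quadrature (ML). There were 1,000 trials per scenario, with Monte Carlo error up to 1.6 points.

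True proportion 89%:

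| σ | Mean excess, PL / ML (points) | Chance above 90%: plain proportion | PL / ML | GLMM passes, plain does not: PL / ML |
|---|---|---|---|---|
| 0.25 | 0.12 / 0.32 | 14% | 19% / 26% | 5% / 11% |
| 0.5 | 0.28 / 0.85 | 19% | 28% / 46% | 8% / 27% |
| 0.75 | 0.68 / 1.80 | 24% | 41% / 72% | 18% / 49% |
| 1.0 | 1.29 / 2.89 | 27% | 59% / 87% | 33% / 60% |

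At a true 88%, the chances of exceeding 90% for the same values of σ are 2, 5, 8 and 14% (plain), 3, 8, 19 and 37% (PL), and 6, 20, 47 and 73% (ML). At σ = 0.25 the variance is estimated at about zero in 36% (PL) to 45% (ML) of trials, so the effect is small. Across 12,000 trials with equal points per subject, the GLMM estimate never failed when the plain proportion passed.

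**Sensitivity.**

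- Section 13.1 expects more than 360 areas. With 24 points per subject the PL excess is 0.1, 0.3, 0.9 and 1.9; ML is unchanged within 0.1.
- With no variance shared across readers, the mean excess is the same within 0.1 point.
- Averaging three reader logits accounts for 0.07–0.12 points of the excess. An intercept-only model (300 trials) isolates the rest: PL 0.05, 0.2, 0.6, 1.2; ML 0.3, 0.8, 1.8, 2.9.
- If compound symmetry is a random-effect structure for readers within subject (PL, 200 trials), the excess is 0.16, 0.36, 0.88 and 1.68.
- With 12 to 24 points per subject, unrelated to accuracy, the mean shift stayed upward. PL fell below the plain proportion in at most 1% of trials, and no pass/fail reversal occurred in 800 trials.

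**The case against.** **The overall estimator is not written down.** The logistic back-transform is stated only per reader; the target is on the overall figure. This stands, and the link to the target is an inference. It is the natural reading of the sentence on the overall estimate. If another rule is meant, the primary estimate is unspecified and still needs text.

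**Compound symmetry could be a residual structure.** If it is purely residual with no random effects, only the 0.07–0.12 points from averaging logits remain. But the section calls the model conditional and includes random effects, which contradicts that reading. Residual compound symmetry together with random effects is possible. A rough PL fit of that combination (150 trials per SD, true 89%) was weakly identified at SDs of 0.25, 0.5 and 0.75. The random-effect variance was about zero in 60–64% of trials and the median excess was about 0.1 point. Where the variance was not zero, the excess was 2–3 points. So the main table does not describe every reading.

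**The shift need not go one way in every trial.** Sections 12.6 and 13.3 allow image counts to vary. When accuracy was assumed to rise with the number of points (12 to 24), PL fell below the plain proportion in 4–29% of trials, and one trial reversed against the GLMM. The mean shift stayed upward and ML never reversed. The absence of reversals in the main runs therefore depends on point counts being equal or unrelated to accuracy.

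**The size is unknown.** This also stands. At SD 0.25–0.5 the excess is 0.1–0.9 points, small beside the 3.1-point half-width. The large contrasts come from high SDs with true accuracy just under the threshold.

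**A GLMM is a recognised choice.** True, but the plan's own definition is the share of points, and this back-transform does not estimate it.

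**Conclusion.** The concern holds and should be fixed. Section 13.2.4 defines one quantity and estimates another, and for any positive random-effect variance and accuracy above 50% the estimated quantity is the higher.

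That this reaches Primary Endpoint 2 rests on the inferred overall back-transform. The size rests on assumed SDs of 0.25 to 1.0 logits, equal-weight points and an unstated fitting method. The pass rates in the table are therefore illustrations, not predictions. The fitting method alone matters: at SD 0.75 and a true 89% it moves the chance of passing from 41% to 72%.

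Confidence is high on direction and medium overall.

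**What to change.** In section 13.2.4:

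1. Define overall accuracy as the population-averaged proportion of points: points earned over points available, pooled over validation subjects and the three readers.
2. Estimate it by binomial GEE with a logit link, working independence, clustering on subject and a small-sample variance correction. Use an intercept-only model for the overall figure. Its estimating equation, Σ(points earned − p × points available) = 0, returns the pooled proportion even with unequal counts. On one balanced simulated data set it returned the plain proportion exactly (0.89074).
3. Apply the >90% target and the overall 95% confidence interval to this estimate.
4. Keep the conditional GLMM as a sensitivity analysis, stating its fitting method, its estimated variance and the block to which compound symmetry applies.

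Integrating the GLMM predictions over the fitted random-effect distribution is an alternative only under ML with quadrature, where the mean difference from the plain proportion was 0.00. Under PL it undershoots by 0.24, 0.58, 1.00 and 1.30 points across the four SDs.

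The cost is SAP wording and a few lines of code, with no new data. Under the assumptions above, with a true 89%, reported accuracy falls on average by 0.1–0.3 points at SD 0.25 and 1.3–2.9 at SD 1.0. The chance of passing also falls when readers truly exceed 90% (400 trials each):

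- True 91%: 83% instead of 88–90% at SD 0.25, and 75% instead of 95–100% at SD 1.0.
- True 92%: 99% instead of 99–100% at SD 0.25, and 92% instead of 98–100% at SD 1.0.

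The overall interval may be somewhat wider.
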